After we obtain the base sample lists from PACDC and CMSL/Marketing, **Business Intelligence & Advanced Analytics** (BIAA), working with PACDC, will pull a dataset to help us determine who meets our inclusion criteria and aid in NIH demographics reporting. This dataset will include demographic information, including patient birth date, race, ethnicity, and gender and/or sex. Finally, the dataset will include death date to ensure patients are living as of the date the data are extracted.

After the intervention is complete, we will obtain experimental outcome data for all population groups from BIAA & PACDC. This will include data on patient flu vaccination, diagnosis of flu, diagnosis of flu-like symptoms, presence of flu-associated complications, hospital visits, emergency department visits, and COVID-19 vaccination status. This dataset will additionally include patient characteristics that can serve as analysis covariates, such as: patient primary care provider and flu-related behavior and outcomes during previous flu seasons.

We may also request claims data from the Geisinger Health Plan (GHP; e.g., for claims related to flu vaccination, diagnosis, and complications). GHP claims data will be pulled by BIAA or the GHP data team (pending approval from Research Contracts).

STUDY DATA DETAILS

Data Management Procedures and Confidentiality

The complete, identified study data will be accessed only by a Geisinger data broker and by limited Geisinger investigators with appropriate training and a legitimate need to know (i.e., Geisinger Co-Is and PIs), and any appropriately trained Geisinger staff, (e.g., clinicians, data analysts) who have a need to review the data for purposes of their normal Geisinger role.

A limited dataset containing dates of service and ZIP codes may be shared with any non-Geisinger collaborators (e.g., [name] and his team) under a Data Use Agreement (pending approval) in compliance with HIPAA's Privacy Rule and using data security protocols reviewed and approved by the Geisinger Security Office, Privacy Office, and Information Technology department.

All data will be electronic. Datasets with full identifying information will only be stored on Geisinger-managed, password-protected computers of the data brokers for the purpose of linking datasets from different sources.

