Nudging Flu Vaccination by Making it Easy for Patients to Schedule a Flu Shot

Statistical Analysis Plan

NCT05493787

1/3/2023

Scientific Background and Objectives

The CDC recommends a flu vaccination to everyone aged 6+ months, with rare exception; almost anyone can benefit from the vaccine, which can reduce illnesses, missed work, hospitalizations, and death. Past work from the study team focused on encouraging flu shots for patients with upcoming appointments. However, many patients in the health system do not have any appointments during flu season.

Eligible patients without an upcoming appointment were randomized to a passive control group (no message), an active control group (a basic message stating that the patient can get a flu shot at Geisinger) or one of several other messages informed by behavioral science ("ease", "waiting for you", "protect yourself - rare outcomes", or "protect yourself - frequent outcomes"). Patients were randomly assigned to one of two message send dates. Messages were sent via patient portal and included a link redirecting patients to a page where they could self-schedule a flu shot.

Methods

Patients eligible for the study as of late October 2022 were randomized to a send date (11/8/22 or 12/6/22) and to one of the following study arms:

1. Passive control: No message
2. Active control: A message that simply stated that patients can get a flu shot at Geisinger
3. Ease: A message that emphasized the ease of getting a flu shot at Geisinger
4. Waiting for you: A message that stated the patient's flu shot was "waiting" for them at Geisinger
5. Protect yourself (rare outcomes): A message that emphasized the rare, dangerous outcomes of getting the flu (e.g., hospitalization, pneumonia), and stated that the flu shot can offer protection from those outcomes
6. Protect yourself (frequent outcomes): A message that emphasized the outcomes that frequently occur in people with the flu (e.g., fever, chills, missing important events), and stated that the flu shot can offer protection from those outcomes

All messages included a link redirecting patients to a page where they could self-schedule a flu shot.

Prior to the second message send date, we removed from the study patients who were randomized to the second send date but were no longer eligible (e.g., because they already received a flu shot or who had an appointment newly scheduled).

The final sample includes 139,503 patients.

Power Analysis

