The sample size above allows 80% power to detect an increase in flu vaccination rates from 35% to 36.24% with two-tailed alpha = .05 for any comparison between message arms.

Project Status

All intervention messages have been sent. Data have not yet been extracted from the electronic health records by the study team.

Planned Analyses

Primary Outcome: *Flu shot self-scheduling* [Time Frame: Within 4 weeks of the patient's message send date]

Secondary Outcome: *Flu vaccination* [Time Frame: Within 4 weeks of the patient's message send date]

We will run the following analyses for both the primary and secondary outcomes:

Question 1: Do any of the message versions increase flu shot self-scheduling or flu vaccination relative to no message?

Analysis 1: We will test the hypothesis that all messages significantly increase self-scheduling and vaccination relative to no message. For each outcome, we will run an OLS regression including a categorical predictor variable coding for each individual arm, with arm 1 (no message) as the baseline.

Question 2: Are any of the messages that contain nudge language informed by behavioral science (arms 3–6) more effective than a simple reminder message (active control, arm 2)?

Analysis 2: We will test the hypothesis that messages in arms 3–6, which contain additional nudge language informed by behavioral science, are more effective than active control messages. For each outcome, we will run an OLS regression including a categorical predictor variable coding for each individual message arm (arms 2–6), with arm 2 (active control) as the baseline.

Question 3: Are the arms that include nudge language (arms 3–6) differently effective at promoting self-scheduling or vaccination?

Analysis 3: For each outcome, we will run an OLS regression with a categorical variable coding for nudge arm (arms 3–6). Pairwise comparisons between arms will be corrected using Tukey's HSD.

Question 4: Is it more effective to send a flu shot message in November or December?

Analysis 4: We will run an OLS regression including a binary variable coding for whether or not the patient was sent a message (no message - arm 1; message - arms 2–5), another binary variable coding for send date, and their interaction.

Sensitivity Analyses and Robustness Checks

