Recent work suggests that OLS regressions are appropriate in randomized experiments with binary outcome variables such as ours (Gomilla, 2021). However, as a robustness check, we will also run the regressions described above as logistic regressions instead of OLS regressions. We may run additional sensitivity analyses or robustness checks.

Other Pre-specified Outcomes

Other Pre-specified Outcomes listed below include flu outcomes (diagnosis, complications) and COVID-19 vaccination. If there are any differences in these outcomes as a function of study arm, the mechanism would almost certainly be increased flu vaccination. Therefore, we will only run analyses on Other Pre-specified Outcomes for analyses above where there is a significant difference in flu vaccination.

1. High confidence flu diagnosis

Patient received a flu diagnosis via a positive polymerase chain reaction (PCR)/antigen/molecular test (yes/no) during the 2022-23 flu season (from the patient's study start date through April 30, 2023).

[Time Frame: Up to 8 months]

2. "Likely flu" diagnosis

Received a "high confidence flu" diagnosis (with positive PCR/antigen/molecular test) and/or "likely flu" diagnosis (as assessed via International Classification of Disease [ICD] codes or Tamiflu administration or positive PCR/antigen/molecular test) (yes/no) during the 2022-23 flu season (from the patient's study start date through April 30, 2023).

Note that "likely flu" is a superset of the "high confidence flu" diagnoses.

[Time Frame: Up to 8 months]

3. Flu complications

Diagnosed with flu-related complications (yes/no) from the patient's study start date through July 31, 2023.

[Time Frame: Up to 11 months]

4. ER visits

Number of ER visits from the patient's study start date through July 31, 2023.

[Time Frame: Up to 11 months]

5. Hospitalizations

Number of hospitalizations from the patient's study start date through July 31, 2023.

[Time Frame: Up to 11 months]

6. COVID-19 vaccination rates

Received at least one COVID-19 vaccination (yes/no) during the 2022-23 flu season (from the patient's study start date through April 30, 2023).

[Time Frame: Up to 8 months]

Additional Exploratory Analyses

1. Difference in message version effectiveness by send date

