The group of patients included in our November message send may differ meaningfully than patients included in our December message send: the group in December had relatively more time to get vaccinated before receiving our messages, but still did not get vaccinated. Therefore, it is possible that which particular message is most effective varies as a function of send date.

To explore this possibility, we will run an OLS regression including message arm (with no message coded as baseline), send date (November, December) and their interaction.

2. Age and gender

Messages might be differently effective as a function of age and gender.

To test the relation between flu shots, age and gender, we will run an OLS regression including binned age (18–24, 25–34, 35–44, 45–54, 65+), gender, and their interaction. We will also test for an interaction between age, gender, and study arm.

3. Patients who opened the messages as a function of message type

We will test whether message open rates vary by experimental arm. Open rates may vary because message subjects varied by experimental arm to correspond to message content. We will run an OLS regression including categorical variable coding for arm number (arms 2–6, the arms that were sent messages) with message open within 4 weeks of the message send date as the dependent variable. We will correct for multiple comparisons using Tukey's HSD.

4. Primary and secondary analyses among patients who opened the message

We will run primary and secondary analyses #2–4 above, limiting our sample to patients who opened their messages within 4 weeks of receiving them. In this analysis, we will also remove from the sample patients who scheduled vaccination appointments or were vaccinated before opening their message.

5. Prior year flu shots

We will test whether patients are more or less responsive to our messages as a function of whether they received a flu shot in the 2021–22 flu season. To this end, we will run an OLS regression with a predictor variable coding for experimental arm, a binary predictor coding for whether the patient received a flu shot in the 2021–22 season, and their interaction.

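### Analyses 1–4 leave out the 2021–22 flu shot as a covariate: a free but small gain in precision on vaccination, plus an unstated standard-error type that matters mainly for the Analysis 4 interaction

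*SAP*

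**What the plan says.** SAP, Planned Analyses. For Analysis 1, "we will run an OLS regression including a categorical predictor variable coding for each individual arm, with arm 1 (no message") as the reference. Analyses 2 and 3 have the same form for arms 2–6 and arms 3–6, with Tukey's HSD for the pairs in Analysis 3. Analysis 4 uses a message indicator, "another binary variable coding for send date, and their interaction". No baseline covariate and no type of standard error is named for any of the four.

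Protocol, Data Sources. The outcome dataset is to hold "patient characteristics that can serve as analysis covariates, such as: patient primary care provider and flu-related behavior and outcomes during previous flu seasons".

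SAP, Additional Exploratory Analyses, item 5. The prior-year shot enters only as an effect modifier: arm, "a binary predictor coding for whether the patient received a flu shot in the" 2021–22 season, and their interaction.

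SAP, Sensitivity Analyses and Robustness Checks: "as a robustness check, we will also run the regressions described above as logistic regressions instead of OLS regressions". Further checks are left open.

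SAP, Power Analysis. 80% power for vaccination of 35% against 36.24%, "for any comparison between message arms".

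**The concern.** The 2021–22 flu shot precedes randomisation, will be obtained anyway, and may well predict vaccination in 2022–23. Leaving such a variable out of the main models gives up some precision. Naming it now also settles whether an adjusted result will be reported, which the plan leaves open.

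Vaccination is the outcome where this could count. The flu, ER, hospital and COVID-19 vaccination outcomes are analysed only where vaccination differs significantly, so power on vaccination also decides whether those analyses are run.

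The second matter is the variance. OLS on a yes/no outcome has unequal variances between cells whenever the rates differ. With equal arms this hardly matters. In Analysis 4 the no-message cell at each date is four or five times smaller than the message cell, and only the December group was thinned: the study team "removed from the study patients who were randomized to the second send date but were no longer eligible". The SAP also notes that "the group in December had relatively more time to get vaccinated before receiving our messages, but still did not get vaccinated", so the rates may differ by date. Which standard error is used could then affect the interaction test.

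**Working it through.** **Inputs from the SAP.** Final sample 139,503; two-sided alpha 0.05; 80% power; 35% vs 36.24%.

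**Assumptions, because the documents give no figures.** Six equal arms, n = 139,503/6 ≈ 23,250. A share π = 0.40 with a prior-year shot. A gap d in the outcome rate between patients with and without that shot. Send dates split 50:50 unless stated. All self-scheduling rates. Write v(p) = p(1−p).

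**1. The plan's own figure.** SE = √[(v(0.35) + v(0.3624))/23,250] = √[(0.2275 + 0.2311)/23,250] = 0.00444. Power = Φ(0.0124/0.00444 − 1.96) = Φ(0.832) = 79.7%. The stated 80% reproduces and corresponds to an unadjusted comparison of two arms.

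**2. Gain from the covariate.** R² = d²π(1−π)/v(p). The SE is multiplied by √(1−R²). For a comparison with exactly 80% unadjusted power, adjusted power = Φ(2.8016/√(1−R²) − 1.96).

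| Outcome rate | Gap d (points) | R² | Power |
|---|---|---|---|
| 10% | 5 | 0.007 | 80.3% |
| 10% | 10 | 0.027 | 81.1% |
| 10% | 20 | 0.107 | 84.2% |
| 35% | 5 | 0.003 | 80.1% |
| 35% | 10 | 0.011 | 80.4% |
| 35% | 20 | 0.042 | 81.7% |
| 35% | 40 | 0.169 | 86.7% |
| 1% (self-scheduling) | 0.5 to 2 | 0.001 to 0.010 | 80.0–80.4% |

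The smaller gaps are more plausible, because everyone analysed was still unvaccinated shortly before the send date.

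**3. Detectable difference at 35% vs 36.24%.** Between two arms: 2.8016 × 0.00444 = 1.24 points, falling to 1.24 × √(1−0.0105) ≈ 1.24 (1.238) for a gap of 10 and 1.22 for a gap of 20.

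For the Analysis 4 interaction with k message arms, the cells at each date are n/2 without a message and kn/2 with one. SE = √{2[v(0.35)/(n/2) + v(0.3624)/(kn/2)]}. With k = 5 this is √{2[0.2275/11,625 + 0.2311/58,126]} = 0.00686, so 1.92 points are needed. Adjustment brings this to 1.91 (gap 10) or 1.88 (gap 20). With k = 4, as Analysis 4 is written, 1.96 becomes 1.95 or 1.92.

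**4. Pooled against correct SE for the interaction.** With the same rates at both dates, ratio = √[s²(1 + 1/k)] / √[v(pc) + v(pm)/k], where pc and pm are the no-message and message rates and s² = [v(pc) + k·v(pm)]/(k+1). Worked case, k = 5, 1% vs 1.5%: s² = (0.0099 + 5 × 0.014775)/6 = 0.01396; ratio = √0.016755/√0.012855 = 1.14.

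| No message vs message | k = 5 | k = 4 |
|---|---|---|
| 35% vs 36.24% | 1.005 | 1.005 |
| 5% vs 6% | 1.06 | 1.05 |
| 1% vs 1.2% | 1.06 | 1.06 |
| 2% vs 2.5% | 1.08 | 1.07 |
| 1% vs 1.5% | 1.14 | 1.13 |
| 0.5% vs 1% | 1.25 | 1.22 |

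The power left from 80% is Φ(2.8016 − 1.96 × ratio): about 76% at 1.06, 71% at 1.14 and 64% at 1.25.

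**5. The other direction.** Dates 60:40, k = 5, message effect +0.5 points at both dates, no-message rate 5% in November. If the December rate is 6%, 7% or 10%, the ratio is 1.011, 0.995 or 0.961 and the actual alpha is about 0.048, 0.051 or 0.060. In the mirror case (10% in November, 5% in December) alpha is about 0.034.

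**The case against.** The strongest reply is that an unadjusted comparison of 139,503 randomised patients is valid and that the improvement is close to nil. At the more plausible gaps, power moves by about one point at most, the Analysis 4 interaction moves from 1.92 to 1.91 points, and the primary outcome is essentially unaffected. The 87% figure needs a 40-point gap that nothing in the documents supports. The protocol says prior-season behaviour can serve as a covariate, which permits its use without promising it. All of this stands, and it sets the priority.

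On the variance, the logistic checks carry the correct binomial variance for the arm comparisons in Analyses 1–3. That stands too. It does not fully cover Analysis 4, because a logistic interaction is on the odds-ratio scale and answers a different question from the OLS interaction.

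A reader might infer that the plan's tests have inflated type I error. The documents do not support this. They do not say that pooled standard errors will be used, and in most of the cases above pooling is conservative. An alpha near 0.06 needs a December no-message rate twice November's, whereas the SAP's description of December patients as people who had still not been vaccinated points, if anything, to lower rates.

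Robust errors are also not free everywhere: Tukey's HSD in its usual form relies on a pooled variance. The arms in Analysis 3 are taken to be equal in size, so little would be gained by changing it.

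**Conclusion.** The omission is real and its effect is small. Under a 40% prior-shot share and equal arms, adjustment lifts 80% power on vaccination to about 80–81% for gaps of 5–10 points and to 82–84% for gaps of 20 points. Self-scheduling gains almost nothing. The unstated variance is secondary: pooled errors for the Analysis 4 interaction would be about 0.5% too wide at the only rates the SAP gives, and about 5–25% too wide at the low rates assumed here.

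A reader might conclude that the unadjusted models are biased, or that the SAP broke a commitment in the protocol. Neither follows: randomisation protects the arm comparisons, and the protocol only makes the covariate available. That the power statement does not cover the interaction is a separate matter, which adjustment does not solve.

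The prior-shot share, the gaps, the self-scheduling rates, the rates by date and the cell sizes are all assumed. This is a free improvement of low priority, not an error.

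**What to change.** **Main change.** Before data extraction, prespecify the 2021–22 flu shot, recorded in the EHR (yes/no), as a main-effect covariate in the OLS models of Analyses 1–4. Report the unadjusted OLS models as a check. State that the logistic checks stay unadjusted; otherwise they would inherit the covariate, and an adjusted odds ratio is a different quantity from an unadjusted one.

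**Optional.** Name HC2 or HC3 standard errors for the Analysis 4 interaction. Analysis 3 with Tukey's HSD can keep its standard variance.

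**Cost.** A few sentences in the SAP, one parameter per model at about 23,250 patients per arm, and one software option. Exploratory analysis 5 already requires the variable, and the SAP's Project Status section says the data had not yet been extracted, so the choice can still be made without sight of the outcomes.

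### Adding a send-date term to Analyses 1–3 would give a small precision gain at almost no cost; the arm contrasts are valid without it.

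*SAP*

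**What the plan says.** SAP, Methods: eligible patients were "randomized to a send date (11/8/22 or 12/6/22) and to one of the following study arms". Before the December send, "we removed from the study patients who were randomized to the second send date but were no longer eligible". The protocol (Detailed Study Procedures) gives passive controls a send date too, so that they can be compared with the patients messaged on that date.

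SAP, Planned Analyses: for each outcome, Analysis 1 will "run an OLS regression including a categorical predictor variable coding for each individual arm, with arm 1 (no message) as the baseline". Analysis 2 uses a "categorical predictor variable coding for each individual message arm (arms 2–6), with arm 2 (active control) as the baseline". Analysis 3 has a categorical term for arms 3–6 only. The logistic robustness check refits the same models. Both outcomes are counted over four weeks from the patient's own send date, so the two date groups are observed over different calendar windows.

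Send date enters in two other places. Analysis 4 has message versus no message, date and their interaction. Exploratory analysis 1 has arm, date and their interaction. The reason given for the latter is that "The group of patients included in our November message send may differ meaningfully than patients included in our December message send".

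**The concern.** Send date is a second randomised factor, known for every patient in every arm. There are two reasons why outcome rates might differ by date: the follow-up windows fall at different points of the season, and only the December group was re-screened after randomisation. If the rates do differ, a model with arm alone counts that difference as residual noise.

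No planned model reports a pooled, date-adjusted contrast for each arm. Analysis 4 merges the message arms. In exploratory analysis 1 the interaction means that, under ordinary reference coding, each arm coefficient is an effect at one date. What is at stake is a little precision, and analysing the trial in line with its own two-factor design.

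**Working it through.** **Inputs from the SAP.** "The final sample includes 139,503 patients", or 139,503 / 6 = 23,250.5 per arm. Equal allocation is an assumption, since no counts by arm or date are given. The power statement claims "80% power to detect an increase in flu vaccination rates from 35% to 36.24% with two-tailed alpha = .05 for any comparison between message arms".

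**Reproducing the plan's figure.** A two-proportion test of 35% vs 36.24% with 23,250.5 per arm and two-sided alpha 0.05 has 79.7% power. Exactly 80% needs 23,411 per arm. The stated 80% reproduces.

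**Assumptions, because the documents are silent.** These are the November and December outcome rates, their gap D, their mean p, and the December share w. No self-scheduling rate is given at all. I take w = 0.5 unless stated.

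**Share of variance due to date.** R² = w(1−w)D² / [p(1−p)]. The SE is multiplied by √(1−R²), and the patient equivalent is about R² × 139,503.

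- 3% vs 1.5%: 0.25 × 0.015² / (0.0225 × 0.9775) = 0.0026. SE falls 0.13%; about 360 patients.
- 10% vs 5%: 0.25 × 0.05² / (0.075 × 0.925) = 0.0090. SE falls 0.45%; about 1,250 patients.
- 15% vs 6%: 0.25 × 0.09² / (0.105 × 0.895) = 0.0215. SE falls 1.1%; about 3,000 patients.

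**At a 35% mean rate.** The unadjusted contrast SE is √(2 × 0.35 × 0.65 / 23,250) = 0.442 points, which gives 80.0% power at 1.24 points.

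| D (points) | R² | SE reduction | Detectable difference (points) | Power at 1.24 points |
|---|---|---|---|---|
| 2 | 0.0004 | 0.02% | 1.239 → 1.239 | 80.0% → 80.1% |
| 5 | 0.0027 | 0.14% | 1.239 → 1.238 | 80.0% → 80.2% |
| 10 | 0.0110 | 0.55% | 1.239 → 1.233 | 80.0% → 80.5% |
| 20 | 0.0440 | 2.2% | 1.239 → 1.212 | 80.0% → 81.8% |

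If the removals leave December with a smaller share, the gain shrinks slightly: at w = 0.3 and D = 10, power reaches 80.4%.

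**Is chance imbalance of dates a separate error?** Take 15% vs 6%. The SD of the difference in date share between two arms is √(2 × 0.25 / 23,250) = 0.0046, and 0.0046 × 9 points = 0.042 points. The unadjusted SE at p = 0.105 is √(2 × 0.094 / 23,250) = 0.284 points. Then (0.042 / 0.284)² = 2.2%, which is the R² already found. The imbalance is part of the unadjusted SE, so the two must not be added.

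**Is the unadjusted test valid?** I simulated 40,000 two-arm comparisons per scenario at w = 0.5.

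- Rates 40% / 30%: null rejection 4.9% unadjusted, 5.0% adjusted; power at 1.24 points 79.5% and 79.8%.
- Rates 45% / 25%: null rejection 5.0% for both; power 79.9% and 81.5%.

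The mean estimates matched the true difference with and without adjustment.

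**The case against.** The strongest reply is that nothing is wrong and the gain is negligible. Most of this stands. Arm was randomised, so the contrasts are unbiased whatever the date split. At the SAP's own 35% rate, even a 10-point date gap moves the detectable difference by only 0.006 points. Neither document says that arm was stratified by date, so the usual rule of adjusting for stratification factors does not apply directly. The SAP says only that the date groups may differ, not that they will.

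A reader might infer more: that date confounds the arm comparisons, or that the December removals unbalanced the arms. The documents do not support this. The stated reasons for removal (a flu shot already received, an appointment newly scheduled) do not depend on arm, and they were applied before the December messages went out. They should not link arm with date beyond chance. Absence of arm-by-date counts is no evidence of imbalance, and the ordinary SE already allows for chance imbalance.

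It can also be said that exploratory analysis 1 covers the matter, because every within-date contrast, including those of Analyses 2 and 3, can be derived from it as a linear combination. That is true of the by-date contrasts. It does not supply a pooled, date-adjusted estimate for the primary and secondary outcomes, and the SAP's general allowance for further sensitivity analyses names none.

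Lastly, the added term is not wholly neutral in the logistic models: it changes the odds ratio from a marginal one to one conditional on date. This stands and should be stated.

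**Conclusion.** The point holds as a minor improvement in precision. Analyses 1–3 omit a factor to which every patient was randomised, and including it could recover a little variance. In the three low-rate scenarios the SE falls by about 0.1% to 1.1%. At a 35% mean rate it falls by 0.02% to 2.2% for date gaps of 2 to 20 points. These figures rest on assumed rates by date, equal arms and a December share near one half. If the dates do not differ, the gain is nil and the cost is one degree of freedom. Neither the validity of Analyses 1–3 nor the stated power is in question.

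**What to change.** Add a send-date main effect to the OLS regressions in Analyses 1–3 and to their logistic versions, and state that the logistic odds ratio is then conditional on date. Report the by-date arm contrasts from exploratory analysis 1 beside the pooled estimates, and give the arm-by-date counts. If the team prefers to keep arm-only models as the main analysis, list the date-adjusted model as a named sensitivity analysis.

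The cost is a sentence or two in the SAP and one term for a variable already held. SAP Project Status says that data had not yet been extracted; the term counts as pre-specified only if it is written in before extraction.

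### Analysis 2 answers an any-of-four question with four contrasts against the active control and states no multiplicity control, so the chance of falsely calling some nudge better is about 7.8% per outcome, not 2.5%

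*SAP*

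**What the plan says.** In the SAP's Planned Analyses, Question 2 reads "Are any of the messages that contain nudge language informed by behavioral science (arms 3–6) more effective than a simple reminder message". Analysis 2 fits one OLS model per outcome with a "categorical predictor variable coding for each individual message arm (arms 2–6), with arm 2 (active control) as the baseline". That model yields four coefficients, for arms 3, 4, 5 and 6 each against arm 2. The accompanying hypothesis is worded differently: "We will test the hypothesis that messages in arms 3–6, which contain additional nudge language informed by behavioral science, are more effective than active control". The section opens with "We will run the following analyses for both the primary and secondary outcomes", so the four contrasts are run on self-scheduling (primary) and again on vaccination (secondary).

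No adjustment, joint test or testing order is given for these contrasts. The SAP's only significance level stands in its Power Analysis: "with two-tailed alpha = .05 for any comparison between message arms".

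Elsewhere the SAP does correct. Analysis 3, on arms 3 to 6 among themselves, says "Pairwise comparisons between arms will be corrected using Tukey's HSD". Item 3 of the Additional Exploratory Analyses, on message opening across arms 2 to 6, says "We will correct for multiple comparisons using Tukey's HSD". Neither statement covers arms 3 to 6 against arm 2 on self-scheduling or vaccination. The protocol describes analysis methods only in general terms and has no multiplicity rule.

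**The concern.** As worded, one winner among four is enough for a yes to Question 2. Four looks at .05 give four chances of a false yes. Whether behavioural-science wording adds anything to a plain reminder is one of the SAP's four planned questions, yet as written it is held to a looser standard than an exploratory comparison of open rates across the same five arms.

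There is a knock-on effect. The SAP analyses the Other Pre-specified Outcomes (flu diagnoses, complications, ER visits, hospitalizations, COVID-19 vaccination) only where an analysis shows a significant difference in flu vaccination. A false positive on vaccination in Analysis 2 would therefore also open that further set of tests.

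**Working it through.** **Inputs.** Final sample 139,503 (SAP, Methods). Six arms. Rates of 35% and 36.24%, 80% power and two-tailed .05 (SAP, Power Analysis). Four contrasts per outcome (Analysis 2). The SAP gives no arm sizes, so equal arms are assumed: n = 139,503 / 6 = 23,250.5 per arm.

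**1. Reproduce the plan's power figure.**
- SE = √[(0.35×0.65 + 0.3624×0.6376) / 23,250.5] = 0.00444.
- 0.0124 / 0.00444 = 2.792.
- Power = Φ(2.792 − 1.960) = 79.7%, which matches the stated 80%.

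The match is for a single contrast with no adjustment. At a Bonferroni level of .0125 the same calculation gives 61.6%. The plan's own power statement therefore treats each comparison as unadjusted.

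**2. Correlation between the contrasts.** All four share arm 2. With n₂ patients in arm 2 and n in each nudge arm, ρ = (1/n₂) / (1/n₂ + 1/n). Equal arms give ρ = 0.5. An arm 2 half the size of each nudge arm gives 2/3, and one twice the size gives 1/3.

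**3. Chance of at least one false finding when all five message arms are truly equal.** With c = 1.96:

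- Either direction: 1 − ∫ [Φ((c − √ρ·x)/√(1−ρ)) − Φ((−c − √ρ·x)/√(1−ρ))]⁴ φ(x) dx
- Nudge better only: 1 − ∫ [Φ((c − √ρ·x)/√(1−ρ))]⁴ φ(x) dx

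| Arm 2 relative to each nudge arm | ρ | Either direction | Nudge better |
|---|---|---|---|
| Half | 2/3 | 13.5% | 6.8% |
| Equal | 1/2 | 15.6% | 7.8% |
| Double | 1/3 | 17.1% | 8.6% |
| Single contrast, for reference | – | 5% | 2.5% |

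With equal arms the ratio to a single contrast is 15.6/5 = 3.1 in either direction and 7.8/2.5 = 3.1 in the nudge-better direction.

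**4. Effect of a Dunnett adjustment.** Setting the either-direction formula to .05 with ρ = 0.5 gives c = 2.442, or p < .0146 per contrast. For vaccination at the SAP's rates:
- Power for one contrast = Φ(2.792 − 2.442) = 63.7%.
- Difference detectable with 80% power = (2.442 + 0.842) × 0.00444 = 1.46 points (35% to 36.46%), against 1.24 points unadjusted.
- Power for at least one of four, if every nudge truly gains 1.24 points, falls from 96.6% to 89.5% (the nudge-better formula with each contrast's mean shifted to 2.792).

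The documents give no base rate for self-scheduling, so the power figures in steps 1 and 4 cannot be carried over to the primary outcome. The error rates in step 3 do not depend on the base rate.

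**The case against.** The strongest counter-argument is that the success rule is ambiguous. The hypothesis sentence in Analysis 2 can be read as a claim about all four nudge messages. If the claim required all four contrasts to be significant, unadjusted testing would not inflate its error. This stands as a condition on the finding. The any-of-four reading is still the more natural one, because the question uses that word, the model reports four separate coefficients, and no rule requires them all to succeed.

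The SAP also never says that the contrasts are uncorrected. That is inferred from its silence, from Tukey being named elsewhere and from a power figure that fits unadjusted .05. If a correction was intended, a sentence is still needed.

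A reader might infer that the false-positive rate for Question 2 is 16% against 5%. That counts nudges that falsely look worse than the reminder, which do not answer a question about being more effective. The matching figures are 7.8% and 2.5%. A reader might also pool the two outcomes and quote a rate above 20%. The SAP already ranks the outcomes as primary and secondary, so the per-outcome rate is the relevant one. Nor does the shared control make the family-wise rate worse: four independent tests would give 18.5%, and sharing arm 2 lowers this to 15.6%.

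Finally, whether distinct messages against a common control need family-wise control is debated, and unadjusted contrasts openly labelled as such would be a defensible minimum. Here, though, the SAP poses the four as one question and corrects comparable families itself.

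**Conclusion.** The point holds, conditionally. If one significant contrast answers Question 2, the plan as written carries about a 7.8% chance per outcome of falsely declaring some nudge better than the active control, roughly three times the 2.5% of a single two-sided .05 test. This assumes equal arms, each contrast tested at the SAP's only stated level, and no true difference among the five messages. The threefold inflation does not hinge on exact equality: with arm 2 at half or twice the size of each nudge arm, the figure is 6.8% or 8.6%. Under an all-four rule there is no inflation.

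The effect estimates from Analysis 2 are unaffected. What is unsupported is the error rate attached to a yes on Question 2. A contrast with p between about .015 and .05 would be significant at the unadjusted level but not within a controlled family.

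**What to change.** In Analysis 2:
- State that one significant contrast answers Question 2.
- Test arms 3 to 6 against arm 2 with Dunnett adjustment (two-sided family-wise .05) from the same OLS model, within each outcome, and report simultaneous confidence intervals. Unadjusted estimates can still be shown if labelled.
- Let the primary outcome decide Question 2. That is self-scheduling, or vaccination if the protocol's fallback applies because self-scheduling cannot be reliably extracted.
- State that the adjusted vaccination result opens the gate to the Other Pre-specified Outcomes arising from Analysis 2.

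In the Power Analysis, state that the 80% figure is for one unadjusted vaccination contrast. Add that for the four Dunnett-adjusted vaccination contrasts, power at 35% versus 36.24% is about 64% and the difference detectable with 80% power is about 1.46 points. State that no such figure is available for self-scheduling without a base rate.

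The cost is a few sentences and a small change to the analysis code. According to the SAP's Project Status, the study team had not yet extracted the data, so the change could have been made before results were seen. The statistical cost is lower power per contrast: about 80% to 64% for one vaccination contrast, but only about 97% to 90% for at least one of four if all four nudges truly gain 1.24 points.
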